Participants must be at least 18 years old, have a diagnosis of HIV, speak and understand English or Spanish, and live in the US. Participants must have a smartphone and be on ART medications. Our participants will all be Medicaid eligible and most of our participants, as can be seen from our preliminary work, are from racial and ethnic minority groups.

To comply with the AHRQ Policy on the Inclusion of Priority Populations (NOT-HS-03-010), our study participants are chronically ill, inner-city, low-income and minority. We anticipate that about 40% of our study participants will include women.

In addition, participants must report past 30 days adherence of 80% or less as measured using the Visual Analogue Scale (VAS)⁶⁷ (Appendix) or have a viral load of over 400 copies/mL. Exclusion criteria are: participation in any other mobile app study for PLWH, not including text messaging studies, and any clinical problems that would not allow someone to use a cell phone. Prior to participating in any study procedure, participants must voluntarily provide informed consent.

D.3. Recruitment Plan.

We will post flyers at each of the recruitment sites listed below and will provide compensation for time that it takes to complete the study questionnaires. The flyer will have the name, contact number, and e-mail for the study coordinator. PLWH from these sites are almost exclusively from low socioeconomic backgrounds. If we are unable to recruit participants after posting flyers, we will then hand distribute flyers to potential participants in the waiting rooms of our sites. We will also be using advertisements through social media that will lead users to a short Qualtrics survey, The Wellness Study Interest Survey, asking for contact information and some eligibility criteria. The purpose of this short survey is to attract more individuals towards our study, provide them with necessary study-related information, and to determine initial eligibility before a staff member reaches back out to screen for enrollment eligibility. Our main sites for recruitment are those where we have previously conducted our studies (HRSA H97HA08483, NINR P30NR010677-03S1 and CDC U01PS003715-01).

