1) The Comprehensive Health Program at Columbia University/NewYork-Presbyterian Hospital provides primary care, HIV specialty care and care coordination services to over 2,000 PLWH. 95% of individuals are of either Black or Latino background and women represent half of the overall population. In addition, the program has 28 direct clinical providers, 8 social workers, and 10 additional care coordinators. Of note, [name] (Co-I) is an attending physician at the Clinic.

2) AIDS Service Center (ASC) is a community based organization for PLWH and persons at risk for HIV. ASC has more than 90 staff, 85 peer interns, and more than 1,800 clients who come for services each year. In addition, another 18,000 people are reached through the peer education and community outreach initiatives of ASC. Given our past experience and success in recruiting participants and using the recruitment strategies described above, we are confident that we will be able to recruit the number of participants needed to conduct the study within the study timeframe. See details in Section A.3.3. Preliminary Work.

STATISTICAL PROCEDURES

D.4. Power and Sample Size.

We will recruit 200 individuals and have greater than 80% power to detect a less than 10% difference in adherence to ART medications between the Wise App and the control group. We assume a 25% attrition rate by the end of trial for both arms. The power calculations are based on the analysis of main outcome, ART adherence. All calculations are based on 2-sided test with alpha at 0.05 level. Our calculations are based on the assumption that each person is on a once daily regimen and the adherence rate is $\leq 80\%$ at baseline.

Many of our participants will be on regimens that are two or three times per day which will provide greater power for our study since we have a greater number of measurements (e.g., 180 for once daily vs. 360 for twice daily regimen). To illustrate, if the adherence rate for the control group does not change, we will have 90.7% power to detect a 6% increase in ART adherence for the intervention group (e.g., from 80% to 86% at

Table 2. Comparison of Intervention vs. Control Group

	Intervention	Control
The Wise App • Medication reminder • Step Goal reminder	✓ ✓	✓
CleverCap™ Lite dispenser	✓	✓

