the end of the trial). If the adherence rate for the control group increases 4%, from 80% to 84% at the end of the trial, we will have 88.6% power to detect a 5% difference in adherence between the intervention and control group. In this case, the intervention group's adherence rate increased an additional 5% (or $4\% + 5\% = 9\%$) from 80% to 89% at the end of the trial.

D.5. Baseline Screening and Assessment.

Potential study participants will complete a phone screening that assesses eligibility. If eligible, participants will attend a baseline session described below.

D.6. Randomization.

Study participants will be randomized (1:1) to Wise App intervention or control arm. We will use a variable permuted randomized block design⁶⁸ where the block size itself is randomly selected (i.e., blocks of four to eight). The advantage of the permuted block design is that treatment assignment is pre-determined before the trial begins and then assignment remains static throughout the course of the trial⁶⁹. Participants will be randomized based on the use of computer-generated random numbers at baseline. The randomization database will be stored on a password protected computer at Columbia University and will only be accessible to [name].

D.7. Procedures.

Upon enrollment in the study, participants will come to the study site, Columbia University School of Nursing to complete consent forms. Following informed consent, study participants will complete a number of baseline questionnaires including socio-demographic characteristics, physical health measurements, behavioral data, health status and social desirability (See Table 3)⁷⁰. Survey instruments will be collected through Qualtrics, a secure, Web-based application designed to support data capture for research studies, providing an intuitive interface, audit trails, and automated export. Qualtrics is a free service offered through Columbia University Medical Center.

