We will also use additional measurements of medication adherence to validate the findings from the CleverCap™ Lite dispenser. We will do blood draws at baseline, 3 and 6 months to measure CD4 and viral load data on each study participant; alternatively, participants will be given the option of providing recent lab results of their CD4 and viral load data. The blood draw at baseline will also be tested for genotyping, GSA chip and qPCR, Hormone blood levels (Estrogen and FSH), and cytokine blood levels (IL-1 β , IL-2, IL-4, IL-6, IL-8, IL-10, IL-13, TNF α , and CRP). The genotyping with GSA chip and qPCR, cytokine blood level and CRP, and hormone blood tests will only be collected once during the course of the study, at Baseline or at the 6-month follow-up if not completed at Baseline. The genotyping, GSA chip and qPCR will be performed by the Feinstein Institute for Medical Research at Northwell Health. We will also ask participants to complete the Center for Adherence Support Evaluation (CASE) Adherence Index, a simple composite measure of self-reported antiretroviral therapy (ART) adherence⁸¹. The CASE Adherence Index consists of three unique adherence questions. Past research has shown that the CASE Adherence Index correlated strongly with the three-day self-reported adherence data ($p<0.001$) and was more strongly associated with HIV outcomes, including a 1-log decline in HIV RNA level (maximum OR=2.34; $p<0.05$), HIV RNA<400 copies/ml (maximum OR=2.33; $p<0.05$) and performed as well as the three-day self-report when predicting CD4 count status. The CASE Adherence Index is an easy to administer instrument that provides an alternative method for assessing ART adherence in clinical settings. Items are scored such that higher values indicate better adherence, and the maximum total score is 16. Scores of 11 or higher on this index indicate good adherence (Cronbach's $\alpha=0.79$)⁸⁶.

Our primary outcome is ART adherence. The CleverCap™ Lite dispenser is our objective measure of ART adherence and the CASE Adherence index as a subjective measure. We are including the subjective measure since there is potential bias in that participants' in the control group may not use the device or may not use the device for the entire study period.

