We will assess for contamination between the study groups at the end of the trial by asking control group participants whether they had used any HIV or medication related apps in the past 6 months. In addition, participants will return at 3 and 6 months to complete the remainder of the measures listed in Table 3 and included in the Appendix. We will also collect data on app use through automated log files so there will not be response burden associated with this measure.

Secondary Outcome Measures: Our measures are listed in Table 3 and included in the Appendix.

D.9. Data Analysis.

We will use intention-to-treat principles for the primary outcome analysis. Intention to treat implies all subjects are considered in analyses. The outcome variable y_{-i} will be the total number of times the CleverCap™ Lite dispenser is opened at day t (from day 1 to day 180) for person i , so y_{-i} follows binomial distribution with parameter of p_{-i} and n where p is probability of taking medication (adherence rate) and n is number of medications to take each day. We use a generalized linear mixed model (GLMM) with logit link function to analyze adherence rate. The basic form of the model is: $\log(p_{-i}/(1-p_{-i})) = \beta_0 + \beta_1 t + \beta_2 t \times \text{INT} + \mu_{-i}$. In the model, μ_{-i} is person level random effect and follows normal distribution. This model is also called individual growth model. Independent variable INT is an indicator for intervention group (INT=1 for the intervention group and INT=0 for the control group). Regression parameter β_1 is change in adherence rate for the control group and β_2 is the difference in change in adherence rate between the intervention group and the control group.

This model can include personal level factors as covariates so we can test for potential confounding by covariates (i.e., age, gender, and health literacy) in this model and inspecting for changes in the point estimate of the relation between study group and adherence.

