We will use GLMM for analyzing secondary outcomes. In our analysis of the surveys related to the SDT framework, the variable time (t) will be at 3 time points (baseline, 3 month, and 6 month) and the link function will be identified for continuous outcomes. In the analysis of app use, the unit of analysis will be at daily level for each participant, and system use will be analyzed using a GMMM with log link function (Poisson model). For the analysis of CD4 and viral load, we will analyze difference-in-difference using GLMM with identity or log link function when these variables are treated as continuous outcomes. Viral load will also be treated as a binary outcome (detectable vs. undetectable) and analyses of viral suppression will use the GLMM with logit link. In a secondary “as treated” analyses, missing adherence and viral load data will be ignored. The genotype analysis will be run by the Feinstein Institute for Medical Research at Northwell Health. Finally, we will assess the relationship between adherence (independent variable) and virologic suppression (dependent variable) using GLMM logistic regression and including missing viral load as detectable. This model will include personal level factors as covariates so we can test for potential confounding by covariates (i.e., age, gender, and health literacy) in this model and inspecting for changes in the point estimate of the relation between study group and adherence.

E. Aim 2b: Assess the acceptability of the CleverCap™ dispenser through In-depth interviews, which will focus on the individual experience of PLWH with the device.

E.1. Sample. At the 3-month follow-up visit, semi-structured in-depth interviews will take place with participants in the intervention group. These participants will be the same participants from the intervention study arm, if they choose to participate (N=100)

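### The primary analysis names no final covariate set, judges covariates by how the arm estimate moves, and leaves out the baseline CASE score and viral load

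*Combined protocol and SAP*

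**What the plan says.** Section D.9 gives the basic primary model as a logistic mixed model with an intercept, time, time by arm and a person-level random intercept. The treatment effect is the time-by-arm coefficient. There is no baseline adherence or viral load term. D.9 then says the model can take person-level covariates (age, gender, health literacy) to test for confounding, by "inspecting for changes in the point estimate of the relation between study group and adherence". It does not say how large a change matters, what follows from one, or which model gives the primary result.

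The sentence returns at the end of D.9 for the model relating adherence to viral suppression, in firmer terms: "This model will include personal level factors as covariates so we can test for potential confounding by covariates". It ends with the same reference to study group and adherence.

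Other sections show what is available at baseline:

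- D.8: "We will do blood draws at baseline, 3 and 6 months to measure CD4 and viral load data on each study participant". Recent laboratory results are accepted instead.
- Table 3: the CASE index is scheduled at baseline, 3 and 6 months.
- Table 3: health literacy is two instruments, the Newest Vital Sign and the S-TOFHLA. D.9 does not say which is meant.
- D.2: for eligibility, "participants must report past 30 days adherence of 80% or less as measured using the Visual Analogue Scale", or else have a viral load above 400 copies/mL. The VAS does not appear in Table 3.
- D.7: the dispenser is handed out after the baseline instruments, so the primary measure has no baseline reading.

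**The concern.** D.6 states: "Study participants will be randomized (1:1) to Wise App intervention or control arm". Under randomisation, any baseline difference between arms is due to chance, so a confounding test is not a sound basis for choosing covariates. Baseline covariates are useful for precision, and the set should be fixed before outcomes are seen. Judging them by movement of the arm estimate makes model choice depend on the result. With three optional covariates there are 2^3 = 8 candidate models. If the literacy instrument is also open and both may enter, there are 2^4 = 16. Nothing in D.9 says which of these carries the primary p-value.

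Two obvious prognostic candidates, baseline CASE and baseline viral load, are not on the list. Two things are at stake: the error rate of the primary test, and any precision lost by leaving baseline out.

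In the adherence-suppression model the repeated wording cannot be applied as written. Adherence is the exposure there and suppression the outcome, so there is no study-group estimate to inspect.

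**Working it through.** **Inputs from the documents.** "We will recruit 200 individuals and have greater than 80% power to detect a less than 10% difference" (D.4). "We assume a 25% attrition rate by the end of trial for both arms" (D.4), so 100 × 0.75 = 75 per arm. "All calculations are based on 2-sided test with alpha at 0.05 level" (D.4). Stated power is 90.7% for 80% vs 86% and 88.6% for 84% vs 89%, with 180 daily measurements per person.

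**Not in the documents, so assumed and ranged.** Between-person variance, within-person correlation (ICC), slope variance, the correlation of baseline with on-trial adherence, and covariate strength.

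**1. The stated power.** Two-proportion normal formula, 80% vs 86%, 75 per arm:

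- One binary result per person: 16.2%.
- 180 independent days per person: about 100%.
- Effective n = 180 × 75 / (1 + 179 × ICC). An ICC of 0.08, solved backwards, gives 13,500 / 15.32 = 881 per arm and power of 91.9%. The same ICC gives 86.7% for 84% vs 89%.

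The stated figures cannot be reproduced from the plan's own inputs because no ICC is given. A single plausible ICC comes within 2 points of both, so they are not shown to be wrong. 90.7% is used below as the starting point.

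**2. Gain from baseline under the written slope model.** The standard error of the time-by-arm coefficient was computed by generalised least squares: 75 per arm, 12 blocks of 15 days, block variance 1/(15 × 0.14) = 0.476 on the logit scale. A baseline main effect with correlation ρ to the person intercept reduces the intercept variance to σ²(1 − ρ²). Grid: σ from 0.5 to 1.5, random-slope SD from 0 to 1.

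Power after adjustment = Φ[(1.960 + 1.322) / (SE ratio) − 1.960], where 1.322 is the normal quantile of 0.907.

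| ρ | SE ratio | Power, from 90.7% |
|---|---|---|
| 0.3 | 0.988 to 0.999 | 90.7-91.4% |
| 0.5 | 0.962 to 0.998 | 90.8-92.7% |
| 0.7 | 0.907 to 0.993 | 91.1-95.1% |

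The gain is about 0-2 points for ρ up to 0.5. A logistic simulation of the written model (300 runs per setting, ρ = 0.5) agrees: the mean standard error fell from 0.0947 to 0.0912 (σ = 0.5) and from 0.1104 to 0.1087 (σ = 1.0).

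**3. Gain if arms are compared on level.** For a person-level analysis of covariance the SE ratio is √(1 − ρ²).

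- ρ = 0.3: 3.282 / 0.954 − 1.960 = 1.48, power 93.1% (+2.4 points).
- ρ = 0.5: 3.282 / 0.866 − 1.960 = 1.83, power 96.6% (+5.9 points).

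**4. Type I error.** Null simulations with 75 per arm and three covariates. Level analysis: 6,000 runs per setting, each covariate correlated 0.1-0.4 with the outcome. Growth model: 1,500-3,000 runs per setting, each covariate correlated 0.2-0.3 with the person intercept.

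| How the result is chosen | Growth model | Level analysis |
|---|---|---|
| Unadjusted | 4.5-5.7% | 4.8-5.1% |
| All three covariates, fixed in advance | 4.3-5.5% | 4.7-5.2% |
| Mechanical 10% change-in-estimate rule | 4.5-5.7% | 3.1-5.2% |
| Smallest p of 8 models | 5.5-6.7% | 6.8-13.1% |

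Simulation standard error near 5% is √(0.05 × 0.95 / runs): 0.3 points at 6,000 runs, 0.4 at 3,000 and 0.6 at 1,500.

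**The case against.** The best defence is that D.9 writes down an unadjusted basic model and says only that covariates can be added. It does not say they will be selected, or that the most favourable model will be reported. A reader might infer that the plan inflates the error rate. The documents do not support that: inflation requires selective reporting that D.9 does not describe, and a mechanical rule showed none. What remains is that D.9 has no mechanical rule and names no primary model, so nothing in it excludes such a choice.

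A reader might also infer a large loss of power, since person-level analysis of covariance at a correlation of 0.5 needs only 1 − 0.25 = 75% of the participants. That figure belongs to a comparison of levels. The written test is of a slope, and the person intercept already absorbs most of what a baseline main effect explains. A correlation of 0.5 is itself not documented. The available baselines are self-report and viral load, eligibility may restrict their range, and D.8 relates CASE to self-report and HIV outcomes but not to dispenser openings.

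Two limits on the remedy also stand. The VAS is documented only as an eligibility screen and may be missing for people who enter on viral load, so it should not be a required covariate. And the adherence-suppression model is observational, so adjusting for confounders there is legitimate; only the copied wording is at fault.

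**Conclusion.** The concern holds as a pre-specification gap that should be closed. D.9 judges covariates in a randomised comparison by movement of the arm estimate, fixes neither the set nor the primary model, and omits baseline CASE and viral load. The possible inflation is modest in the written growth model (5.5-6.7% at worst over the settings tried) and larger (about 7-13%) only if levels were compared and the best of 8 models reported. The precision argument is secondary: about 0-2 points of power under the written model for correlations up to 0.5, and about 2-6 points at 0.3-0.5 for a level comparison. All of these sizes rest on assumed variances, correlations and covariate strengths, because the documents give none. The wording fault in the adherence-suppression model needs no assumption.

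**What to change.** 1. In the primary analysis of D.9, delete the change-in-estimate step.
2. Name one primary model with a fixed covariate set, kept whatever the results: baseline CASE score, log10 baseline viral load, age, gender, and one named health-literacy instrument. State that these values are taken before allocation, since D.6 and D.7 do not order the two explicitly.
3. State a simple rule for missing baseline values, including viral load supplied from recent laboratory results.
4. Report the unadjusted model as a sensitivity analysis.
5. In the adherence-suppression model, keep the pre-specified covariates but remove the reference to study group and adherence. Word the sentence for an adherence exposure and a suppression outcome.

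The cost is a revision of D.9, a few extra model terms and some missing baseline values to handle. No new data collection is needed.

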The Wise App will motivate and engage participants over time. Although mHealth technology may be promising, several studies have shown that adherence to mHealth interventions is low and decreases over time ⁴³, even though these studies showed a significant effect on health outcomes ⁴⁴. Therefore there is a need for strategies that motivate people to use, and keep using, the technologies offered. Gamification, the use of game-like rewards and incentives, paired with desired behaviors, is one such strategy that can be used to increase motivation to sustain habits of individuals over time ⁴⁵. Companies have widely accepted and adopted gamification as a means to increase initiation and retention of desired behaviors ⁴⁶. In fact, it has been estimated that 60% of health initiatives in workplaces now include gamification elements ⁴⁷. PatternHealth Technology's HealthStar mobile app, referred throughout this protocol as "The Wise App," will use persuasive games to motivate end-users ⁴⁸. End-users can set health and fitness goals and use persuasive gaming to help meet the goal. In the case of the Wise App, participants will set goals, have a tally bar, and receive reminders to motivate them to complete their goals.

mHealth tools, including mobile apps, for PLWH have not been well-developed or evaluated.

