Given the dearth of useful and likeable apps ⁵⁴, the need for improving medication adherence in PLWH and the great promise that mHealth holds, we propose to test a smartphone app linked to a smart pill box called CleverCap™ Lite (The Wise App) for PLWH targeting ART adherence and guided by a rigorous and relevant theoretical framework⁵⁵. The feasibility of the Wise App is supported by data demonstrating that use of mobile devices is nearly ubiquitous in the U.S. with persons from underserved groups being more likely to own a smartphone and more likely to use a smartphone (as compared to a computer) to access the Internet. The current trial is significant in representing one of the first principled and systematic efforts to build a mHealth app intervention based on user-centered design work and linked to a smart pill box for improving health outcomes. Our proposed study, based on our empirical findings from our preliminary work ⁵⁶⁻⁶¹, uses rigorous methods and a theory-based approach ⁵⁵ to develop and test a mHealth intervention (Wise App) for improving ART adherence for PLWH.

STUDY DESIGN

The goal of this study is to test the efficacy of The Wise App for improving health outcomes (as measured by improving ART adherence) in PLWH. Our secondary outcomes are: (a) healthcare access (b) technology

acceptance (c) technology use. Table 1 presents and overview of the design, participants and data analysis plan for each aim.

Table 1. Overview of Design, Methods, Participants, and Data Analysis			
Aim	Design/Methods	Participants	Data Analysis
1	Cognitive Walkthrough, and user testing using think-aloud protocol	Cognitive Walkthrough: human-computer interaction experts (N=5); User testing: PLWH (N=30)	Quantitative and qualitative summary of heuristic violations; thematic analysis of think-aloud protocol, quantitative summary of mouse clicks, time, etc.
2	Randomized controlled design	PLWH (N=200; intervention=100, control n=100) for 6 months	Descriptive statistics; Linear regression model
2b	In-depth Interviews	PLWH (N=100; intervention group only)	Qualitative coding of in-depth interviews related to CleverCap device; thematic analysis to examine CleverCap experience and acceptability
3	Descriptive: focus groups	Focus groups: Participants in the intervention arm of the RCT (N~50)	Descriptive, thematic analysis to examine post-intervention perceptions related to The Wise App use, usefulness and impact on overall health

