Following the completion of the baseline study instruments, study participants in both arms will be given a CleverCap™ Lite dispenser and trained on how to use it, as well as a fitness tracker that will be synced to Wise App. Study participants in both arms will be trained by study team members on how to use the different features of the Wise App. Those in the intervention group will receive medication reminders while those in the control group will receive reminders about completing their step goal. Participants in both arms will be given a document that includes contact information for the project team, information about compensation, study reminders, and will also receive a telephone call from a research assistant 1 week after enrollment to assist with any technical problems with the app or the CleverCap™ Lite dispenser and biweekly thereafter.

Participants will be texted appointment reminders for study visits via Qualtrics. Hard to reach participants will also be sent scheduling reminders through the Qualtrics system and encrypted e-mails from the study's secure CUMC e-mail address.

Token of appreciation: Participants will be given \$40 at the baseline visit, \$50 + up to an extra \$25 for app challenges completed at the 3 month visit, and \$60 + up to an extra \$25 for app challenges completed at the 6 month visit (up to a total of \$200 for participation) and for providing a blood sample (or recent lab results) for viral load/ CD4 testing and completion of study questionnaires. Participants will also have the option to have the cost of their transportation to and from the study site paid for, through a ridesharing service.

D.8. Operationalization of Outcome Measures.

The primary outcome will be ART adherence, measured by the CleverCap™ dispenser. The CleverCap™ dispenser will automatically record each time a participant opens the dispenser. We will collect adherence data each day from the start to the end of trial (day 1 to 6 months), and it is a count response (number of times taking medication each day). Frequency of app use will be counted each time a participant opens the app.

Table 3. Study Measures

Tool		Measurement Time Points
Demographic Variables and Potential Confounders		
Socio-demographic characteristics	Gender, age, education, income, employment, health insurance, housing	Baseline
Behavioral Data	Use of condoms, tobacco, alcohol, substance use	Baseline, 3 and 6 months

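### Daily app opens are assigned a Poisson mixed model with no stated safeguard; if the adherence model's form is carried over, the time-by-arm test of app use can reject far too often

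*Combined protocol and SAP*

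**What the plan says.** The Study Design section lists technology use among three secondary outcomes ("acceptance (c) technology use"). Section D.8 defines the measure: "Frequency of app use will be counted each time a participant opens the app". For the analysis, D.9 says that "the unit of analysis will be at daily level for each participant" and that "system use will be analyzed using a GMMM with log link function (Poisson model").

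For app use, D.9 goes no further. It does not list fixed effects or random effects, name the arm term to be tested, or say how overdispersion, day-to-day correlation or differing personal trends will be handled.

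The one model equation in D.9 belongs to the adherence outcome and is offered as a basic form. It has an intercept, time, time-by-arm and a single person term, which "is person level random effect and follows normal distribution". There is no arm main effect, so the time-by-arm coefficient is the only arm term; it "is the difference in change in adherence rate between the intervention group and the control group". D.9 labels this an individual growth model, but the equation contains no person-specific slope.

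**The concern.** A Poisson model fixes the day-to-day variance within a person at that person's mean. With a single person-level intercept it also gives everyone in an arm the same time trend and treats the days as independent once the intercept is known. With up to 180 days per person, the within-person information then looks very large and the standard error of a slope contrast very small. If opens cluster on some days, or people drift away from the app at different rates, that standard error is too small.

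The protocol has features that make such departures plausible: payments for app challenges tied to the 3- and 6-month visits, support calls at one week and then biweekly, and an assumed 25% attrition. At stake is a reported difference between arms in how app use changes over time that may be no more than an artefact of the variance assumption.

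**Working it through.** **Is there a stated figure to reproduce?** No. The documents give no mean, variance, power or error rate for app use. The power figures in D.4 concern adherence and do not bear on this point.

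**Inputs from the documents.** 200 participants (D.1), randomized 1:1 (D.6), 25% attrition (D.4): 100 × 0.75 = 75 per arm. 180 daily records per person (D.9, stated for the dispenser and applied here to app use). Two-sided alpha of 0.05 (D.4, stated for adherence).

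**Step 1, analytic.** If the within-person variance is φ times the mean, the model standard error of a within-person contrast is too small by a factor √φ. The true type I error is then 2 × (1 − Φ(1.96/√φ)).

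| φ (assumed) | √φ | 1.96/√φ | Type I error |
|---|---|---|---|
| 2 | 1.41 | 1.39 | 17% |
| 3 | 1.73 | 1.13 | 26% |
| 5 | 2.24 | 0.88 | 38% |

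**Step 2, simulation with no arm difference.** 75 per arm, 180 complete days, 600 trials per scenario. The model was a random-intercept Poisson fitted by maximum likelihood (adaptive Gauss-Hermite quadrature), with a Wald test at 0.05. The Monte Carlo standard error at 5% is √(0.05 × 0.95/600) = 0.9 points. Assumptions not in the documents: 1.5 opens a day at the start, mean log-rate change of −0.7 over six months, random-intercept SD of 1, and every departure in the table. Here k is the negative binomial dispersion (variance = mean + k × mean²), and slope SDs are on the log scale over six months.

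| Scenario | Model SE of slope | True SD of slope | Time-by-arm rejection | Average-level rejection | Time-by-arm, person-clustered SE |
|---|---|---|---|---|---|
| Poisson assumptions hold | 0.032 | 0.032 | 3.5% | 4.5% | 3.8% |
| Overdispersion, k = 0.3 | 0.032 | 0.050 | 21% | 5.8% | 7.3% |
| Overdispersion, k = 1 | 0.032 | 0.076 | 40% | 3.8% | 7.5% |
| Personal slopes, SD 0.2 | 0.032 | 0.059 | 28% | 5.3% | 5.7% |
| Personal slopes, SD 0.5 | 0.032 | 0.137 | 62% | 5.7% | 6.2% |
| Personal slopes, SD 1.0 | 0.030 | 0.307 | 84% | 5.3% | 8.2% |
| Autocorrelated days, rho 0.9, SD 0.7 | 0.032 | 0.212 | 77% | 5.3% | 9.5% |
| k = 1 and slope SD 1.0 | 0.030 | 0.339 | 84% | 5.2% | 10.0% |

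The last column uses the conditional (within-person) Poisson slope with a person-clustered standard error. Adding an arm main effect to the model changes the time-by-arm rejection rate by at most 1 point in any row.

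**Step 3, consistency check.** The rejection rates follow from the standard-error ratios. For slope SD 0.2, 0.059/0.032 = 1.84, and 2 × (1 − Φ(1.96/1.84)) is about 29%, against 28% simulated. For k = 1, 0.076/0.032 = 2.38 gives 41%, against 40%.

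**Step 4, why average level is safe.** That comparison is between persons. With random-intercept SD 1 its standard error is close to √(2 × 1²/75) = 0.163, and the fitted value with k = 1 was 0.163 against a true SD of 0.157. The estimated person variance absorbs the extra variation, so the error rate stays near 5%.

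**The case against.** The strongest reply is that D.9 never says the app-use model has only a person intercept. The single person effect and the time-by-arm contrast are written for dispenser adherence, and a statistician fitting app use could add a random slope. That stands, so the point is conditional. But D.9 fixes the Poisson distribution for app use and supplies no other template, so the written route leads to the vulnerable test.

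A reader might infer that every arm difference in technology use will look significant too often. The documents do not support that: no contrast is written for app use, and a comparison of average level kept 3.8% to 5.8% error in every scenario.

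A reader might also take the rationale section as the protocol's own forecast of uneven decline. It says only that "several studies have shown that adherence to mHealth interventions is low and decreases over time", which describes other studies and is given as the reason for gamification. A decline common to all would be absorbed by the fixed time term. The harm comes from people differing in their trends, and the section is silent on that.

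Finally, every variance, autocorrelation and slope input above is assumed. If the data meet the Poisson assumptions, there is no inflation. That also stands.

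**Conclusion.** The point holds in conditional form. The plan commits app use to a daily Poisson mixed model with no stated protection. If the adherence model's form is carried over, the time-by-arm test is anti-conservative under overdispersion, autocorrelation or differing personal trends. Its size is a range set by assumption: about 17% to 38% for variance/mean ratios of 2 to 5, and about 21% to 84% across the simulated departures, against about 4% with none. The simulation assumed complete records for 75 per arm and did not model dropout.

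This is a worthwhile, cheap improvement to one secondary outcome. It says nothing against the primary adherence conclusion, and it would be wrong to read it that way.

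**What to change.** In D.9, state the arm contrast for app use: average level or time-by-arm. For a time-by-arm contrast, make person-clustered robust standard errors the default. They brought the error rate down to about 6% to 10%; a small excess remains in the harsher scenarios. Name a negative binomial mixed model with a person intercept and a random time slope as the supporting analysis. It was not simulated here and does not by itself model day-to-day autocorrelation, which is why it should not be the default.

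The cost is a sentence or two in D.9 and a small code change, with no new data. The price is wider intervals for app use.
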